We have designed a three arm RCT (figure 2, below), with each arm varying as to who gets access to the audio after the visit and who is aware of the fact that audio recording is occurring during the visit. The design establishes the conditions for achieving the first two aims of the study, with each aim framed as testable hypotheses. Arm 1 is the intervention, with both provider and patient aware of the recording. It is designed to represent how OAA would be utilized in actual practice. In Arm 2 all parties are also aware of the audio recording, but this time neither gets access to the audio after the visit (although the research team does). Arm 2 is a control for isolating the effect of patient access after the visit to the audio in Arm 1. Both patient and physician are blind to whether they are in Arm 1 or 2 until after the visit. Comparing these two arms will achieve the first aim of the study. Arm 3 is a second kind of control, as the audio is again not shared with the patient. In this arm, however, the patient conceals the audio recorder, typically in an accessory such as an eye glass case (a method we have employed extensively¹⁴), so that the provider is unaware they are being audio recorded until after the visit, enabling the research team to achieve the second aim of the study by comparing Arm 3 to Arm 2, isolating the effect of being aware they are being audio recorded on the provider's interactions with the patient. Whereas in Arm 3 the physician is unaware they are being recorded, in Arms 1+2, they are aware and also know there is a 50% chance the patient will have access to the audio. This design enables Arm 2 to serve both as a control for Arm 1 to achieve Aim 1 (since patient only gains access to the audio in Arm 1) and as comparator with Arm 3 – to achieve Aim 2 -- since the physician believes the patient may gain access to the audio.

[figure not shown]
Figure 2: Study Design

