The superscripts associated with each outcome in the “How Answered” boxes in figure 2 refer to the following strategies for testing the hypotheses in Aims 1 and 2: (a) A survey called the Patient Activation Measure (PAM), (Appendix A-1) is completed by patient 1-2 weeks after their visit²²; (b) The “no show rate” is the inverse of Return Visit Adherence (RVA) rate;²³ (c) the Refill rate is “proportion of days covered” (PDC), a metric CMS utilizes in its plan ratings;²⁴ and (d) BP and HgB A1c are checked if they are repeated within 6 months; (e) The SEGUE Framework for evaluating and scoring communication behavior, as rated off of the audio recording by a research assistant utilizing a checklist (Appendix A-2)²⁵ and (f) Content Coding for Contextualization of Care, also called “4C”²⁶. Note: (b-d) are extracted from the CDW and SEGUE and 4C completed while accessing the medical record and listening to the audios. Finally, for all three arms, the members of the research team collecting the data and coding the audio are blinded as to study arm. There is no arm in which the patient is unaware a visit is audio recorded. Blinding the patient is not pertinent to achieving the aims of the study.

Figure 3, the flow diagram below, allocates patients in a parallel three arm randomized controlled trial (RCT) to most efficiently achieve the aims of the study (the calculations for the specific sample sizes are justified later in the protocol – and shown in Tables 4.1 and 4.2. on pp 24+25).

Figure 3: Flow diagram for parallel RCT

Random assignment to arms will be made using computer-generated sequences within the diabetes clinics (1:1 randomization to Arms 1 and 2 in blocks of 4) and primary care clinics (5:5:2 randomization to Arms 1, 2, and 3, in blocks of 24, with one partial block of 8 patients). Solid lines represent unconditional allocation of participants to Arms; dashed lines represent random sampling of participants to create efficient unbiased subsamples for key hypothesis tests. The rationale for the design, starting at the top of the figure and working down, is as follows:

- We start with two separate pools, diabetes and primary care clinics, because measurement of the effect of OAA vs control (Arm 1 vs Arm 2) on Hgb A1c is most efficiently accomplished

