Isolating the effect of the OAA on providers requires including an arm in which the provider is unaware of the recording, but which the research team can analyze, to serve as a control. This will occur in Arm 3 (figure 2), in which the audio will be carried and concealed by the Veteran so that the provider is not aware of it. As in Arm 2, neither Veteran nor provider will have access to the audio after the visit, but the research team will be able to listen to it. This will enable comparisons of provider behavior (communication and contextualization of care) in Arm 3 (control) with Arm 2. Although the patient will not actually obtain the audio in Arm 2 after the visit, the physician does not know that, as at the time of the encounter they are blinded as to whether they are in Arm 1 (in which the patient will gain access to the audio) or Arm 2 (in which they will not).

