For the audio recording device, we plan to use VHA approved audio recorders with accompanying software, the DS-9000 and DS 9600 Olympus encrypting recorders with a pin code for security. The audios will be uploaded by the RA to a workstation desktop on to our secure VHA research server, hosted in our Center of Innovation (COIN), using the VHA approved Olympus/ODMS Dictation Module 7. Each audio file name will include the Veterans last name and date of the visit., for Arm 1), The project manager will then trim the audio to remove all the identifiers using the audacity software and upload the deidentified audio directly to the HealthPAL website(<https://va.audiohealthpal.com>) managed by the research team at the

Department of Biomedical Data Science at the Geisel School of Medicine at Dartmouth. At that point an automated script sends an email to the patient and provider (in Arm 1) providing them a link to login to access the audio from any internet enabled device. The Dartmouth system, HealthPAL,²¹ which is specifically designed for sharing audios with patients, also enables patients to selectively share their audio with others, such as family or caregivers, using a highly secure process that enables them to send an invite email and text message with a six digit code, that enables the user to set up their own unique password. This feature additionally enables the research team to track how patients are using audios including whether they are listening to them, how often, whether they share them and whether those individuals access the audios as well. Because many of the patients at participating sites are older and have low levels of technology literacy, we will make an attempt to reach by phone any subject who has not accessed HealthPAL within 7 days following their visit. These data will be variables in our analysis for the outcomes in Aim 1, e.g. for patient activation, medication adherence etc...

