(C) Upon arrival, they will complete the informed consent process and the brief literacy screen (REALM-SF), receive the audio recording device, and instructions based on the arm of the study to which they are randomized, as to whether to keep the audio recording out in the open (Arms 1 and 2), or to conceal it (Arm 3). A code, assigned to the encounter, will be utilized as the ID on the literacy screen, and linked to the patient name and medical record number stored in the cross walk file on a separate VHA approved server. After the encounter, patient and provider participants will receive a link to access the audio if they were in Arm 1. If they are called prior to completing the process, their appointment takes precedence and they will not participate.

(D) In addition to pre-visit outreach, the RA will recruit patients at an information desk on site when they arrive in the waiting area with a poster and a brochure inviting Veterans to learn more if they are interested.* This will occur until recruitment targets are met. Those who are seeing a participating provider and want to participate will complete the informed consent process and the brief literacy screen (REALM-SF). They will receive a \$20 gift card to remunerate them for the additional work of completing the survey after the visit and for randomly participating in a follow up call for the PAM survey. If the Veteran is called prior to completing the process, their appointment takes precedence and they will not participate.

***COVID-19 MODIFICATION: As long as infection transmission remains a risk the following protocol modification will be in place:**

- Only phone based recruitment will occur.
- The informed consent process will be completed over the phone prior to the visit, except for the final signing process.
- The RA will still meet the patient in the waiting area, both masked. However, it will be a very brief meeting and they will remain 6 feet apart. There will be a small fold

up table in the waiting area. The patient will sign the consent form, collecting the audio recorder, and complete the 7 item REALM-SF which consists of reading out loud 7 words, and takes less than 1 minute.

- Post visit, the patient will return the audio recorder to the table and collect \$20 gift card from the research assistant. Again, the RA will maintain a physical distance of at least 6 feet and will remain masked.

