As noted earlier, the PAM will be completed over the phone by the RA initially at one week after the visit (this will be extended to 10-14 days if it turns out a substantial number of patients listen to the audio more than one week after the visit).

Table 4.1 lists the calculated power for the intention-to-treat analyses for Hypotheses 1A-1C by outcome. These analyses are based on data from 1029 combined primary care and diabetes clinic visits each in Arms 1 and 2 (i.e. sample size 2058), except for measuring the effect of OAA on Hgb A1c (in 1C) which is based only on 202 diabetes clinic visits each in Arms 1 and 2 (total 404). For patient activation (1A), we assume veterans with no audio access will have a mean PAM score of 56 and standard deviation of 19.5, based on a 2016 national study of VA health care users;³⁵ clinically meaningful differences in activation have been described as 4-6 points.³⁶ Since testing hypothesis 1A requires a phone call to administer the PAM, we will randomly contact 924 participating subjects, an average of 9 calls/week across sites, which will achieve 80% power, instead of calling all 2058 subjects. Baseline rates of each undesirable outcome for 1B are derived from our previously published study in the VA using recordings without provider awareness or patient access (as in Arm 3), and we expect to find an odds ratio of 0.5 for each outcome when patients have access to audios.¹⁴ Baseline rates of each undesirable outcome for 1C are derived from the data warehouse (Chicago and Cleveland facilities – see table 3, above).

Table 4.1: Expected differences and power for planned intention-to-treat analyses for hypothesis 1A-1C

Hypothesis	Outcome	Baseline without audio available	Expected with audio available	Sample size	Power

		(Arm 2)	(Arm 1)	(total)	
1A	Patient activation (PAM 0-100 score)	56.0	60.0	924	80%
1B	Visit no-show rate	7%	4%	2058	95%
	Medication Proportion of days not covered	13%	7%	2058	80%
1C	Hgb A1c > 8 with repeat in < 6 Mo	66-70%	33-35%	404	80%
	Most Recent SBP>140 or DBP>90* with repeat in < 6 Mo	39%	24%	2058	99%

Also, while not included in Table 4.1, because it is not a primary objective of Aim 1, we will explore whether OAA is associated with fewer ED visits and hospitalizations. With the current sample size, we will in fact have 80% power to detect a decrease in inpatient admissions from 14%, the 2018 rate in our study population, to 9%.

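### In the diabetes clinics, fixed 1:1 blocks of 4 with Arm 1 disclosed after each visit leave the physician's in-visit blind partly predictable, and no allocation concealment is described

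*Combined protocol and SAP*

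**What the plan says.** Section 5.1 makes the blind a condition of the design: "Both patient and physician are blind to whether they are in Arm 1 or 2 until after the visit". Later in that section the reason is given for the provider: "at the time of the encounter they are blinded as to whether they are in Arm 1". The belief the provider should hold in the open-recorder arms is also stated; they "also know there is a 50% chance the patient will have access to the audio".

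The same section specifies the allocation. In the diabetes clinics it is "1:1 randomization to Arms 1 and 2 in blocks of 4"; in primary care it is "5:5:2 randomization to Arms 1, 2, and 3, in blocks of 24, with one partial block of 8 patients". The block sizes are fixed and printed in the protocol.

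Section 5.2, item (C), has the patient consent on arrival, take the recorder and receive "instructions based on the arm of the study to which they are randomized". The rest of that sentence limits the instruction to whether the recorder is kept in view (Arms 1 and 2) or hidden (Arm 3). The diabetes clinics have no Arm 3, so every patient there gets the same instruction.

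Disclosure follows the visit. Under the audio technology heading in section 5.1, the RA uploads each recording to the VA server, and the project manager trims the Arm 1 recordings and loads them to the sharing website. Then: "At that point an automated script sends an email to the patient and provider (in Arm 1". If no link comes, the visit was in Arm 2.

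**The concern.** The protocol itself expects providers to behave differently when a patient may replay the visit. Arm 2 holds that effect constant only while the physician's expectation of access is the same in both arms. Small fixed blocks combined with disclosure after each visit work against this, because each revealed assignment changes the odds of those remaining in the block. A physician, or an RA preparing the patient, who can foresee Arm 1 could act differently. Part of any A1c difference would then come from the visit and not from access to the recording.

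The early assignment also serves no purpose. Nothing before or during a diabetes clinic visit depends on whether the patient is in Arm 1 or Arm 2.

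**Working it through.** **Inputs.** Block size 4 at 1:1 (section 5.1); "202 diabetes clinic visits each in Arms 1 and 2 (total 404" patients (section 5.6); intended chance of Arm 1 of 50% (section 5.1). The number of providers per sequence, the delay before the link arrives, and whether each site has its own sequence are not given, so they are treated as assumptions.

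**The plan's own figure.** 404 / 4 = 101 complete blocks, and 101 × 2 = 202 per arm. This reproduces. Before anything is revealed, the chance of Arm 1 is 50%.

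**Upper bound: all earlier assignments seen, in order and at once.** A block holds two of each arm. The observer guesses the arm with more places left.

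| Position in block | Chance of a correct guess | Chance the arm is certain |
|---|---|---|
| 1 | 1/2 | 0 |
| 2 | 2/3 | 0 |
| 3 | 1/3 × 1 + 2/3 × 1/2 = 2/3 | 1/3 |
| 4 | 1 | 1 |

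- Correct: (1/2 + 2/3 + 2/3 + 1) / 4 = 70.8%, about 286 of 404.
- Certain: (1/3 + 1) / 4 = 33.3%, about 135 of 404.

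This observer need not know where blocks begin, because a running count from the start of the sequence returns to zero at the end of each block.

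**Lag in disclosure, one observer who knows the block boundaries.**
- One-patient lag: positions 1 and 2 give 1/2. Position 3 is guessed from position 1 (2/3). Position 4 is guessed from positions 1 and 2 (2/3). Correct: (1/2 + 1/2 + 2/3 + 2/3) / 4 = 58.3%. Certain: (1/3) / 4 = 8.3%.
- Two-patient lag: (1/2 + 1/2 + 1/2 + 2/3) / 4 = 54.2% correct, none certain.

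**Providers who see only their own patients, no lag, boundaries known (simulation).**

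| Providers sharing the sequence | Correct | Certain |
|---|---|---|
| 2 | 59.9% | 8.2% |
| 3 | 57.0% | 3.8% |
| 5 | 54.4% | 1.3% |
| 10 | 52.4% | 0.3% |

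If the boundaries are unknown and the provider relies on a running count of their own patients, two to four providers give only about 51% to 53% correct.

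**What each remedy achieves against a full observer.**
- Drawing Arm 1 or 2 after the visit from the same blocks: unchanged, 70.8% correct and 33.3% certain.
- Blocks varied over 4, 6 and 8 with sizes hidden: about 68% correct (simulation).
- Blocks varied over 8, 12 and 16: about 64% correct (simulation).
- Simple 1:1 randomization: 50% correct, none certain. The standard deviation of an arm's size is √(404 × 0.5 × 0.5) = 10.05, so 202 plus or minus about 10.

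**The case against.** The blind in section 5.1 binds the patient and the physician. A patient recruited for one visit sees no sequence, and a physician who shares a sequence with colleagues learns little. The observer with most to gain would be the RA, whose view of the sequence is not documented. Section 5.1 says that team members who collect data and code audio are blinded to arm, and the upload that identifies Arm 1 is the project manager's task. The link is sent only after upload, trimming and a second upload, so immediate disclosure is a worst case. Most patients are approached by mail and telephone before the visit, which limits selection at the desk. A concealment procedure may also exist in the Data Analysis Plan mentioned in section 6.0 or in parts of the document not available here.

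Most of this stands, and it lowers the likely size. A reader might infer from the section 5.2 sentence that the RA or patient knows Arm 1 from Arm 2 at hand-over. The text does not support that, since the instruction separates only open from concealed recorders. Nor does the text show that the RA sees the ordered sequence. Handling access problems, and the planned call to patients who have not logged in within 7 days, would identify some Arm 1 patients to whoever does this, but late and incompletely.

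The structural point remains. The provider is told the outcome of each past assignment in their own patients, the block size is fixed and small, and the sections on randomization and recruitment do not say who holds the list or from whom it is hidden.

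**Conclusion.** The point holds as a partly predictable blind with a cheap remedy. The figures of 33% certain and 71% guessable are upper bounds, which require every earlier assignment to be seen in order and without delay. A lone provider with a one-patient lag would be right about 58% of the time and certain in 8%. With two or three providers per sequence and block boundaries known, the figure is about 57% to 60%; with boundaries unknown there is little gain. Provider numbers and e-mail delays are assumptions, and a separate sequence per site would raise predictability by putting fewer providers on each.

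A reader might conclude that the blind is in fact broken or that the A1c comparison is biased. The documents show neither. They show a scheme that allows prediction, no described safeguard against it, and no need for the Arm 1 or 2 assignment before the visit. Primary care is less exposed: within a block of 24, with full knowledge, Arm 1 versus Arm 2 is guessable 61.7% of the time and certain in 9.1%.

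**What to change.** 1. Before the visit, assign only open or concealed recorder. In the diabetes clinics all are open, so no draw is needed at that stage.
2. After the recorder is returned, have the computer assign Arm 1 or Arm 2 and release the result only to the project manager who loads Arm 1 audio. Withhold it from the recruiting RA.
3. Replace the fixed blocks of 4 with simple 1:1 randomization, or with large, randomly varied blocks whose sizes appear in no document open to site staff or providers.
4. State in sections 5.1 and 5.2 who holds the sequence and from whom it is concealed.

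Steps 2 and 3 must go together. Deferring the draw alone leaves the block arithmetic unchanged, and varying the blocks over 4, 6 and 8 alone leaves about 68% guessable. Simple randomization is the cleaner choice because providers will still receive the Arm 1 links and could otherwise learn from them.

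The cost is a change to the randomization program, a paragraph of protocol text and a possible small imbalance in arm sizes (about 202 plus or minus 10 under simple randomization). No extra patients, visits or staff are needed.

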5.3 Informed Consent Procedures

- Indicate if informed consent will be obtained and/or if you are requesting a waiver of informed consent or waiver of documentation of informed consent. If the research involves multiple phases, specify for which phases of the research the waiver(s) is being requested and/or the informed consent will be sought.
- Describe who will be obtaining informed consent, if applicable, and any circumstances that may need to be addressed (e.g. subjects with impaired decision making ability and the use of a legally authorized representative, etc.)
- If applicable, indicate how local site study personnel will be trained regarding human subjects protections requirements and how to obtain and document informed consent.

Providers: As described in recruitment section above, participating physicians and nurse practitioners will complete an informed consent process. As noted, those who wish to participate will sign a sheet providing their name and contact information. The site investigator and/or RA will meet with them to complete the informed consent process.

Patients: As described in recruitment section above, prior to participation but upon arrival for their appointment, patients will complete the informed consent process. As noted, the RA will meet patients (who have already assented by phone) prior to their appointment to complete the consent process.

All personnel will complete all mandatory VA training for human subject research and have current certificates.

Hospital Leaders: As explained above, we plan to interview hospital leaders about the program. They are also subjects, but given the low risk to them, we have requested for a waiver of documentation of consent. We will be contacting them via email asking them to participate in the research study by attaching the Informed consent explaining the research study and their participation..

5.4 Inclusion/Exclusion Criteria

- Describe the criteria that determine who will be included in or excluded from the study.

There is no plan to exclude any category of patients in participating clinics who wish to participate and complete the informed consent process. Women and minorities will be included. There is no plan to include children in this study.

Hence we plan to include individuals who consent from the following groups:

Patients who seek medical services at either the primary care clinics or the diabetes clinic; Providers who are either physicians or independent practitioners such as Advance Practices Nurses in these clinics; and hospital leaders whose portfolio of responsibilities includes management or oversight of clinical care.

5.5 Study Evaluations

- Describe all evaluations to be conducted (including screening; tests/questionnaires that will be administered; any procedures that subjects will be required to complete) and data collection methods. Include materials as an appendix or separate attachment.

There will be several sources of research material. Instruments are included in appendices A-1 through A-8 as indicated below and as attached:

- A) Audio recordings of encounters made with written consent by both patients and providers. The audios are collected for research purposes.
- B) The patient's medical record: Following a 10% (n=250) random sample of audio recorded visits (arm 3), again with written patient subject consent, a trained coder will extract discrete pre-determined variables for "4C" coding from the medical record after the visit, based on the referenced 4C manual.
- C) Phone calls to a random (40%) sample of patients to complete the Patient Activation Measure.
- C) Surveys of all patients (a brief literacy screen), and of both patients (25% of encounters) and all providers about their experience participating in an OAA program. (for patients: A-1, A-7, A-8; for providers: A-2, A-3).
- D) Provider focus groups about their experience participating in an OAA program. (A-4, A-5)
- E) Structured interviews with facility leaders about their experiences with the OAA program. (A-6)

